2.1 Study setting

The study will be conducted in the Cardiac Intensive Care Unit (UTIC) of the University Hospital (AOU) of Parma, a highly specialised public teaching hospital integrated with the University of Parma and located in the Emilia-Romagna region, Italy.

The UTIC of the AOU Parma is a high-intensity care setting characterised by multidisciplinary and continuous management of critically ill patients with acute cardiovascular diseases (e.g. acute myocardial infarction, decompensated heart failure, severe arrhythmias). In this context, different professionals work in an integrated way: cardiologists (clinicians, interventional cardiologists, electrophysiologists), nurses, healthcare assistants (OSS), physiotherapists, pharmacists, university students and newly hired staff, whose interprofessional interaction is crucial for quality of care.

2.2 Eligibility criteria

2.2.1 Inclusion criteria

Participants meeting all of the following criteria will be included in the study:

- Healthcare professionals (physicians, nurses and healthcare assistants/OSS) employed in the Cardiac Intensive Care Unit (UTIC) of the University Hospital of Parma.
- Healthcare professionals who have completed the training pathway and are still working in the unit at the time of the six-month follow-up.
- Medical and nursing students who have carried out or are carrying out a clinical placement within the UTIC.
- Ability to use a computer or mobile device, essential for participating in the online training activities (e.g. Moodle, H5P).
- Provision of written informed consent before initiation of any study procedure.

2.2.2 Exclusion criteria

Participants meeting one or more of the following criteria will be excluded from the study:

- Healthcare professionals who do not work in the cardiology setting or who are not employed in the UTIC of the AOU Parma.
- Inability to participate in the training activities or assessment sessions for logistical, organisational or clinical reasons (e.g. planned prolonged absences during the study period).
- Refusal or inability to provide informed consent.

No patients will be involved, as simulations will be conducted with the healthcare professionals participating in the study, after obtaining their consent to take part.

2.3 Interventions

2.3.1 Experimental intervention – Training phase

The training phase of the project consists of an interactive course aimed at healthcare professionals (physicians, nurses and OSS) to improve their ability to recognise and enact effective collaborative practices. Learning is based on the use of **branching scenarios**, created with the H5P software. This approach enables learners to distinguish correct practices and refine their teamwork skills. The course also provides access to additional content on techniques and procedures specific to the UTIC context, curated by expert professionals.

Branching scenarios – Learning scenarios

The branching scenarios reproduce complex and frequent clinical situations that challenge interprofessional collaboration. Each scenario has been designed with particular attention to clinical and organisational details, including:

- the clinical history of the simulated patient and their clinical pathway in the cath-lab and electrophysiology unit, in preparation for a TAVI procedure, with a diagnosis of heart failure (Annex 1);
- vital signs and diagnostic tests;
- available resources;
- clinical objectives and potential critical points.

The structure of each scenario includes:

- definition of a storyline and of the role of the professional involved;
- division into key phases, with information and possible actions, and the related consequences;
- interactive elements that enable the learner to make decisions and interact with characters or objects in the scenario;
- meaningful feedback guiding the learning process;
- multiple paths for a dynamic experience;
- assessment criteria based on the correctness of the responses.

For validation and revision of these scenarios, a team of content experts and educationalists was involved to verify the accuracy, relevance and effectiveness of the material. Pilot tests with sample users were also carried out to collect feedback on usability and clarity, and the necessary modifications were implemented.

Four training pathways are planned, each lasting six months:

1. Cath-lab pathway
2. Electrophysiology pathway
3. Heart failure pathway
4. TAVI pathway

For further details on the structure of the pathways, see Annex 8 “Pathway Sheets”.

Platform and technical implementation

For the management of contents and simulations, the **Moodle Self-PA** platform has been chosen. This platform, specifically designed for the Emilia-Romagna Regional Federation, is an online learning environment dedicated to the continuing education of public administration professionals in the region.

The Federated Regional Moodle Self-PA Emilia-Romagna represents a key resource for strengthening the skills and knowledge needed to face the challenges of the public sector. Thanks to its flexibility and numerous features, it is an effective tool to promote a culture of learning and professional development within the region.

Professionals will be trained to make the best use of the platform’s potential, using interactive tools such as Lessons, Quizzes, Forums, Wikis and SCORM packages. To manage more complex interactions, branching scenarios and virtual tours created with H5P and integrated directly into Moodle will be used.

The technical implementation of the Moodle platform has included:

- configuration of SCORM packages;
- uploading of teaching materials;
- definition of navigation and assessment rules.

Extensive testing was conducted to ensure proper platform functioning, optimal display of contents, consistency of narrative flow and accurate recording of learners’ data.

Documentation and learner guide

A comprehensive documentation set has been produced, including a detailed guide for learners. This guide provides clear instructions on how to use the scenarios, explains the learning objectives and describes the assessment methods (Annex 2). The guide will be distributed before the beginning of the training pathway.

2.4 Endpoints

Description of endpoints, instruments, measurement units and frequency

- **Attitudes towards interprofessional collaboration**
 - Instrument: *Jefferson Scale of Attitudes toward Physician–Nurse Collaborative Relationships (JSAPNC)*.
 - The instrument consists of 5 dimensions: (1) shared education, (2) teamwork, (3) caring vs. curing, (4) nurse autonomy, (5) physician autonomy. It includes 15 items on a 4-point Likert scale from 1 = “strongly agree” to 4 = “strongly disagree”.
- **Perception of collaboration**
 - Instrument: *Nurse–Physician Collaboration Scale (NPCS)*.
 - The scale consists of 3 dimensions: (1) joint participation in the care-related decision-making process; (2) sharing of patient-related information; (3) cooperativeness. It includes 20 items on a 5-point Likert scale (1 = always, 2 = usually, 3 = sometimes, 4 = rarely, 5 = never).
- **Decision-making**
 - Instrument: *Collaboration and Satisfaction with Care Decisions (CSACD)*.
 - The tool measures collaboration between physicians and nurses in decision-making about patient care in relation to a specific patient. It consists of 8 items: the first seven measure interaction, and the last measures satisfaction with the decision-making process, on a 5-point Likert scale from “strongly disagree” to “strongly agree”.
- **Team and professional commitment**
 - Instrument based on items adapted from Ellemers et al. (1995), Cadinu & Reggiori (2002) and Le Blanc et al. (2010).
 - Total of 17 items: 12 items for **professional commitment** (e.g. “In general, I am happy to be part of my professional category”) and 5 items for **team commitment** (e.g. “I am satisfied to be a member of this unit/team”), on a 5-point Likert scale from 1 = strongly disagree to 5 = strongly agree.
- **Self-efficacy**
 - Instrument: “Personal accomplishment” subscale of the *Maslach Burnout Inventory (MBI)*, Italian adaptation by Vanin & Castelli (2003) and Sirigatti & Stefanile (1993), based on Maslach & Jackson (1981).
 - Composed of 5 items evaluating perceived competence and personal accomplishment at work, using a 5-point Likert scale from 1 (strongly disagree) to 5 (strongly agree). Example item: “I feel very competent in my work.”

Data collection for these endpoints will occur at three time points: before the start of the training (T0), at the end of the training (T1), and six months after completion of the programme (T2).

2.5 Study duration

The study will start after approval of this protocol by the Ethics Committee and authorisation by the Directorate of Health Professions, and will continue for 24 months.

2.6 Sample size

A convenience sample will be used, consisting of professionals who agree to participate in the training process (planned: physicians: 5; nurses: 30; OSS: 8; nursing students: 5; medical students: 5).

2.7 Recruitment

On the training days, the Principal Investigator or a delegate will present the project and request informed consent from physicians, nurses, OSS, medical students and nursing students affiliated with the UTIC of the University Hospital of Parma.

3. Methodology: data collection, management and analysis

3.1 Data collection

Data collection will take place at three distinct time points for each participating healthcare professional. Data will be collected via the Moodle Self-PA platform, after each participant has provided informed consent. Before accessing the platform, the information sheet and consent form will be provided. Subsequently, the professional will be able to access the questionnaire through the link provided. At the end of the questionnaire, a code will be requested for cross-matching, which must be generated as follows: initial of the mother's first name, mother's year of birth in four-digit format, and participant's own year of birth, also in four-digit format. Assessments will be carried out in three phases: before the start of the training pathway, at the end of the training and six months after completion of the pathway. The first assessment (T0) will take place before the start of the training event, the second (T1) at the end, and the third (T2) six months after the conclusion of the training event. The instruments used for attitudes, perception of collaboration, decision-making, team/professional commitment and self-efficacy are those described in section 7.4. Before starting the study, adequate training on the use of the scales and instruments will be provided to the assessors. The data sheets generated via the dedicated Moodle platform, accessible only to professionals participating in the study, will then be processed. These pseudo-anonymised data will be accessible exclusively to the Principal Investigator and their delegates and will be stored on a password-protected personal computer of the University Hospital of Parma. In case of a data breach, the folder path will be changed and the members of the study team indicated in the protocol will be asked to change their password.

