3.2 Data analysis

- **Reliability and validity:** At T0, T1 and T2 Cronbach's alpha and McDonald's omega will be calculated for each (sub)scale. Where appropriate, the factor structure will be confirmed through confirmatory factor analysis (CFA) with assessment of measurement invariance (configural → metric → scalar) prior to longitudinal comparison.
- **Data preparation and quality:** data cleaning, coding, reverse-scoring of items; exploration of missing data, outliers and distributions (histograms, Q–Q plots); inspection of floor and ceiling effects; documentation of the data dictionary.
- **Descriptive analysis and responsiveness:** descriptive statistics for T0, T1 and T2 (mean, SD, median, IQR) for total and subscale scores. Suggested graphs: spaghetti plots (individual trajectories), box/violin plots and mean lines with 95% CI over time. Responsiveness to change: calculation of Cohen's d (T1–T0; T2–T0; T2–T1) and Standardized Response Mean (SRM) as indices of change, with interpretation according to literature conventions; where possible, definition/search of MCID.
- **Main analysis – Linear mixed models (LMMs):** For each outcome, a linear mixed model will be used with time as a within-subject factor.
 - Dependent variable: continuous outcome score.
 - Fixed effects: Time (T0 as reference; levels T1, T2).
 - Random effects: random intercept for participant; if data allow, random slope for Time.
 - Covariance structure: unstructured or AR(1) for equally spaced measures; REML estimation.
 - Planned contrasts: T1–T0 (immediate effect), T2–T0 (maintenance), T2–T1 (decay/maintenance).
 - Effect measures: standardised β , marginal and conditional R^2 ; conversion to d from LMM estimates with 95% CIs.

- Assumptions/diagnostics: normality of residuals and homoscedasticity; graphical inspection and robust tests in case of violations.
- Covariates (recommended): age, seniority, profile (physician, nurse, OSS, student/new hire), concurrent educational exposures.
- Interactions: Time × Profile; Time × Seniority, to analyse differential impacts.
- Clustering: if relevant (e.g. shifts/teams), addition of a group-level random effect.

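### The only stated link between T0, T1 and T2 is a short self-generated code that may be entered inconsistently; the loss would be partial and is cheap to prevent

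*Protocol*

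**What the plan says.** Section 3.1 states the linkage method outright: "At the end of the questionnaire, a code will be requested for cross-matching, which must be generated as follows", namely "initial of the mother's first name, mother's year of birth in four-digit format, and participant's own year of birth, also in four-digit format". It is the only means of matching that the protocol names. No assigned study number, list of valid codes, duplicate check or confirmation step is described.

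The same section says "Data collection will take place at three distinct time points for each participating healthcare professional". The code closes a questionnaire given at T0, T1 and T2, so re-entry at each wave is a sound inference, though the text does not say it in so many words. Section 2.3.1 gives each pathway six months and section 2.4 puts T2 six months after completion, so T0 and T2 lie about 6 + 6 = 12 months apart.

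In section 3.2, "a linear mixed model will be used with time as a within-subject factor", with "Random effects: random intercept for participant". The planned contrasts compare T1 with T0, T2 with T0, and T2 with T1. Section 1.5 limits the evaluation to professionals who finished the training and are still in the unit at six months, and places the socio-demographic variables at T0.

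Section 2.6 gives the numbers: "planned: physicians: 5; nurses: 30; OSS: 8; nursing students: 5; medical students: 5". They sum to 53, of whom 43 are staff and 10 students.

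Section 3.1 has the data collected through Moodle. Sections 3.3 and 5.5 have them collected first on paper and then digitised, and 5.5 has the paper forms destroyed afterwards.

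**The concern.** The code can fail in two ways.

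- **Duplicates.** The code carries little information. Students' birth years fall in a narrow band, a mother's birth year tracks her child's, and one initial adds little. Two people with the same code may be merged, which adds false pairs and lowers the apparent within-person correlation.
- **Inconsistent entry.** The participant must give the same nine characters three times over about a year, including a parent's birth year. One slip splits a person into two apparent participants.

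The within-person contrasts, the standardised response means and the individual trajectories in 3.2 all use the link. A completer whose T2 code differs from the T0 code can look lost to follow-up, in a study whose evaluation is restricted to completers.

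Repair is also harder than it needs to be. Variables that could settle a doubtful match are stated as collected at T0 only. If paper is used, transcription adds a second source of error and the source forms are then destroyed.

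**Working it through.** The protocol states no match rate, error rate or power, so there is no figure of its own to reproduce. The sample comes from 2.6: 5 + 30 + 8 = 43 staff and 5 + 5 = 10 students, 53 in all. Every other input below is an assumption.

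**1. Duplicates.** Assume staff born evenly over 1962–2000 (39 years), students over 1999–2004 (6 years), mother's age at birth normal with mean 28 and SD 4.5, and 20 possible initials.

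- Expected pairs sharing own birth year:
  - staff: (43 × 42 / 2) / 39 = 903 / 39 = 23.2
  - students: (10 × 9 / 2) / 6 = 45 / 6 = 7.5
  - mixed (overlap 1999 and 2000): 430 × 2 / (39 × 6) = 3.7
  - total: about 34.3
- Chance that such a pair also shares the mother's birth year: 1 / (2√π × 4.5) = 0.063.
- Chance of the same initial: 1/20 = 0.05 if all are equally likely, or 0.104 under one skewed distribution.
- Expected duplicate pairs: 34.3 × 0.063 × 0.05 = 0.11, or 34.3 × 0.063 × 0.104 = 0.22.
- Chance of at least one, 1 − exp(−expected): 10% and 20%.

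Simulation with 20,000 replicates on these birth-year inputs gave 10% (equal initials) and 19% (skewed initials), with 0.11 and 0.21 duplicates expected. Varying the inputs (staff born from 1960, 1975 or 1985 up to 2000; mother's age mean 29 and SD 4 to 6) gave 8–22% with equal initials and 15–40% with skewed ones. The expected number of people affected was 0.16 to 1.0. The 40% needs the narrowest staff age band, the smallest SD and skewed initials together.

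**2. Inconsistent entry.** Let *e* be the error rate per entry, independent between waves and never repaired.

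- All three records match: (1 − *e*)³.
- A given pair of waves matches: *f* = (1 − *e*)².

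| *e* | All three match | Of 53 | Of 43 staff | A given pair matches |
|---|---|---|---|---|
| 2% | 0.941 | 49.9 | 40.5 | 0.960 |
| 5% | 0.857 | 45.4 | 36.9 | 0.903 |
| 10% | 0.729 | 38.6 | 31.3 | 0.810 |

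**3. Precision of T1–T0.** Let ρ be the within-person correlation, assumed 0.5 to 0.8. If unlinked records stay in the model as different people, the variance of the difference, in SD units, is 2(1 − ρ) / {N[1 − ρ(1 − *f*)]}. The standard error relative to perfect linkage is therefore 1/√[1 − ρ(1 − *f*)]. If unlinked pairs are dropped, the ratio is 1/√*f* = 1/(1 − *e*).

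| *e* | Kept, ρ = 0.5 | Kept, ρ = 0.8 | Dropped |
|---|---|---|---|
| 2% | 1.010 | 1.016 | 1.020 |
| 5% | 1.025 | 1.041 | 1.053 |
| 10% | 1.051 | 1.086 | 1.111 |

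For example, at *e* = 10% and ρ = 0.8: 1/√(1 − 0.8 × 0.19) = 1/√0.848 = 1.086. The ratios do not depend on N, so they hold for 43 as for 53.

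**4. Small profiles.** At *e* = 10%, the expected number with a broken chain is 5 × 0.271 = 1.4 physicians and 8 × 0.271 = 2.2 OSS. These are the groups that feed the Time × Profile interaction in 3.2.

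**The case against.** Six points can be made for the plan as it stands.

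- **A mixed model does not need three linked waves.** This stands. A reader might infer from the table that, at 10% error, 43 staff shrink to 31. That requires listwise deletion across all three waves at the worst assumed rate. Section 3.2 plans no such deletion, and 1.5 defines completers by training and employment, not by a matching code.
- **The error rates have no source, and the formula is pessimistic.** This stands in part. A birth year wrongly believed but always entered the same way still links, and in a group of 53 some one-digit slips could be resolved by near-matching.
- **Duplicates are rare and visible.** This stands. Fewer than one is expected, and two identical codes within one wave would be noticed if someone looked.
- **Anonymity has value.** In a unit with five planned physicians, staff who rate collaboration with colleagues may answer more freely when no list ties names to answers. The protocol does not give this reason, but the choice is defensible and the remedy should respect it.
- **A platform identifier cannot be assumed.** This stands. Section 3.1 says "The data sheets generated via the dedicated Moodle platform, accessible only to professionals participating in the study, will then be processed", and a reader might infer that a Moodle user ID is ready for linkage and merely unused. The text says only who has access. Nothing says that responses carry a user ID, and 3.3 and 5.5 describe paper first.
- **Handling of unmatched records may sit in an analysis or data-management plan that is not shown.** True, and its absence is not held against the protocol. But 3.1 itself fixes the key, and later handling rules can only partly mend a weak one.

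**Conclusion.** The point holds in a limited form. The protocol fixes a fragile key as its only stated link for an analysis built on within-person change. It should be strengthened before T0, because mismatches are hard to repair afterwards.

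The likely cost is modest: a few percent on the standard error, reaching about 9% with unlinked records kept, or 11% with them dropped, only at a 10% error rate. To this are added some completers who may wrongly appear lost at T2. Inconsistent entry drives this, and duplicates matter little. The sizes rest on assumed error rates, correlations, birth years and initials, and on re-entry at each wave, which is inferred. The point does not show that the primary contrasts fail, since mean change over time can still be estimated from unlinked records. It is a cheap improvement of minor to moderate severity.

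**What to change.** **In section 3.1:** issue each participant a unique random study ID at consent and use it at all three waves, whether the questionnaire is on paper or in Moodle. Any key should be held by someone outside the analysis team. Unique IDs cannot collide, and a mistyped one can be checked against the issued list. This fits the pseudonymised status already declared in 3.1, 3.3 and 5.5.

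**If the self-generated code is kept to protect anonymity:** show it back for confirmation, check for duplicates at T0, and ask profession and gender at every wave as a second match key. Adding more typed characters is not the remedy, since it addresses the smaller risk and gives more chances for error.

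**In either case:** reconcile the Moodle collection in 3.1 with the paper forms in 3.3 and 5.5, because the route decides where codes are entered and whether a mismatch can be traced.

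**Cost:** a few lines of protocol text, and either a key to safeguard or two repeated items at T1 and T2. Profession and gender are already recorded at T0, so repeating them asks for no new kind of personal data.

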3.2 Data analysis

- **Reliability and validity:** At T0, T1 and T2 Cronbach's alpha and McDonald's omega will be calculated for each (sub)scale. Where appropriate, the factor structure will be confirmed through confirmatory factor analysis (CFA) with assessment of measurement invariance (configural → metric → scalar) prior to longitudinal comparison.
- **Data preparation and quality:** data cleaning, coding, reverse-scoring of items; exploration of missing data, outliers and distributions (histograms, Q–Q plots); inspection of floor and ceiling effects; documentation of the data dictionary.
- **Descriptive analysis and responsiveness:** descriptive statistics for T0, T1 and T2 (mean, SD, median, IQR) for total and subscale scores. Suggested graphs: spaghetti plots (individual trajectories), box/violin plots and mean lines with 95% CI over time. Responsiveness to change: calculation of Cohen's d (T1–T0; T2–T0; T2–T1) and Standardized Response Mean (SRM) as indices of change, with interpretation according to literature conventions; where possible, definition/search of MCID.
- **Main analysis – Linear mixed models (LMMs):** For each outcome, a linear mixed model will be used with time as a within-subject factor.
 - Dependent variable: continuous outcome score.
 - Fixed effects: Time (T0 as reference; levels T1, T2).
 - Random effects: random intercept for participant; if data allow, random slope for Time.
 - Covariance structure: unstructured or AR(1) for equally spaced measures; REML estimation.
 - Planned contrasts: T1–T0 (immediate effect), T2–T0 (maintenance), T2–T1 (decay/maintenance).
 - Effect measures: standardised β , marginal and conditional R^2 ; conversion to d from LMM estimates with 95% CIs.

- Assumptions/diagnostics: normality of residuals and homoscedasticity; graphical inspection and robust tests in case of violations.
- Covariates (recommended): age, seniority, profile (physician, nurse, OSS, student/new hire), concurrent educational exposures.
- Interactions: Time × Profile; Time × Seniority, to analyse differential impacts.
- Clustering: if relevant (e.g. shifts/teams), addition of a group-level random effect.

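### Does pairing a participant random intercept with an unstructured covariance spoil the planned mixed model?

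*Protocol*

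**What the plan says.** Section 3.2 of the Protocol describes one linear mixed model per outcome. Time enters as a three-level factor: "Fixed effects: Time (T0 as reference; levels T1, T2". The random part is "Random effects: random intercept for participant; if data allow, random slope for Time", so the intercept is unconditional and only the slope is guarded. The next line reads "Covariance structure: unstructured or AR(1) for equally spaced measures; REML estimation" and does not say whether it describes the residual matrix or the matrix of the random effects. The contrasts are T1–T0, T2–T0 and T2–T1. The effect measures include "marginal and conditional R^2" and a d derived from the model estimates.

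Section 3.1 fixes the number of assessments: "Data collection will take place at three distinct time points for each participating healthcare professional". They fall "before the start of the training pathway, at the end of the training and six months after completion of the pathway". Section 2.3.1 adds "Four training pathways are planned, each lasting six months".

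**The concern.** AR(1) and equal spacing are properties of repeated measurements, so the natural reading of the covariance line is the residual matrix. An unstructured residual matrix already reproduces every variance and covariance between assessments. A participant intercept on top of it adds a parameter about which the data carry no information.

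The fit may then fail to converge or report a singular Hessian. If it does converge, the reported share of variance due to participants is not determined by the data. Conditional R-squared is built on that share, so a planned effect measure would have no fixed value. A d scaled by the residual SD would suffer in the same way. All of this can be seen before any data are collected.

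**Working it through.** **Inputs.** Three assessments (section 3.1). Time as a factor, an unconditional random intercept, and unstructured or AR(1) covariance (section 3.2). Planned numbers in section 2.6: "planned: physicians: 5; nurses: 30; OSS: 8", which is 43 staff, plus 5 nursing and 5 medical students, 53 in all. The Protocol gives no correlations, SDs, means or missing-data rates on this point, so those below are assumptions. It also gives no figure of its own to reproduce.

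**1. Parameter count.** The likelihood depends on the covariance only through V = σb²·J + R, where J is the 3×3 matrix of ones. V has 3·4/2 = 6 distinct elements. The rank is that of the Jacobian of those 6 elements.

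| Structure | Parameters | Rank |
|---|---|---|
| Unstructured residual, no intercept | 6 | 6 |
| Intercept + unstructured residual | 7 | 6 |
| Intercept + per-level Time slopes (unstructured) + residual variance | 7 | 6 |
| Intercept + per-level Time slopes (diagonal) + residual variance | 4 | 4 |
| Intercept + linear slope (unstructured) + residual variance | 4 | 4 |
| Intercept + AR(1) residual | 3 | 3 |

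The redundancy does not come from having only three assessments. With k assessments an unstructured R has k(k+1)/2 parameters, equal to the number of distinct elements of V, so an added intercept is always one too many.

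**2. How far the split can move.** For a given V, any σb² from 0 to 1/(1'V⁻¹1) leaves R = V − σb²·J a valid covariance matrix. With unit variances and assumed correlations T0–T1 / T0–T2 / T1–T2:

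- 0.7/0.5/0.7: upper bound 0.743
- 0.6/0.36/0.6: 0.667
- 0.6/0.5/0.6: 0.709
- all 0.6: 0.733

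**3. Effect on the results.** Data were simulated for 53 participants with 10 missing at T2, SD 1 and means 0, 0.4, 0.3. The unstructured V was fitted by REML and then split at several values of σb². With F the variance of the fitted time means and S the average total variance, marginal R² = F/(F+S) and conditional R² = (F+σb²)/(F+S).

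| Assumed correlation | −2 REML log-likelihood | Marginal R² | Conditional R² |
|---|---|---|---|
| 0.3 | 117.842527 at every split | 0.108 | 0.108 to 0.573 |
| 0.5 | 97.445129 at every split | 0.061 | 0.061 to 0.606 |
| 0.7 | 44.047546 at every split | 0.057 | 0.057 to 0.776 |

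At correlation 0.5 the contrasts T1–T0, T2–T0 and T2–T1 were 0.527, 0.104 and −0.423, with standard errors 0.126, 0.164 and 0.134, at every split. A T1–T0 d on the total SD stayed at 0.59; scaled by the residual SD it ran from 0.59 to 0.91. A separate simulated set with n = 43 gave the same pattern: log-likelihood −143.5631 throughout, T1–T0 0.451 (SE 0.110), marginal R² 0.040, conditional R² 0.04 to 0.75.

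**4. The AR(1) option.** A six-month pathway followed by a six-month follow-up gives spacings of 6 and 6 months, so AR(1) is usable for one pathway, and with an intercept it is identified. It does not make the intercept share precise. At n = 43 over 2,000 simulated trials, with the four correlation sets in the order of step 2, the central 95% of estimated shares was 0–0.67 (true 0.10), 0–0.57 (true 0), 0–0.68 (true 0.47) and 0.25–0.74 (true 0.60).

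**The case for a change.** The best case for a change is that this is not left to a later document. Section 3.2 itself states an unconditional intercept, an unstructured covariance and conditional R-squared. Reading unstructured as the random-effects matrix is not a clean escape either: Time is a factor, and per-level slopes with that matrix again give 7 parameters for rank 6. A sentence now would also stop an analyst choosing a structure after a failed fit on real data.

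The algebra stands in full, and so does the extension to a residual-scaled d. Three things limit it.

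- The defect needs a reading the text does not state. A linear slope with an unstructured random-effects matrix and independent residuals is identified, and the slope is fitted only if the data support it.
- The redundant model is one permitted choice, not a required one, because AR(1) stands in the same line.
- Arbitrary here means between marginal R-squared and an upper bound set by V. The checks imposed several splits; they did not test whether different software or starting values return different answers.

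The concern about choosing a structure late carries little weight for the main results. Every split of the redundant model gives the same contrasts and standard errors. A singular Hessian could disturb the small-sample degrees of freedom, but it would also be a visible warning that prompts a simpler fit.

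**Conclusion.** No change is needed. This is a gap in wording that an analyst will fill sensibly. Read one way, section 3.2 permits a model with one redundant covariance parameter, and conditional R-squared then has no fixed value: 0.061 to 0.606 at an assumed correlation of 0.5. The same line permits an identified model, and the quantities on which conclusions rest (the three contrasts, their standard errors, marginal R-squared and a d on the total SD) are the same under every split, provided the fit converges. Section 5.9 judges success by perception of collaboration and attitudes to teamwork; nothing in the Protocol is decided by conditional R-squared.

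Nor would a rewrite gain much. Even the identified AR(1) model leaves the intercept share nearly undetermined in three of the four assumed settings at n = 43. Replacing the random intercept with a purely unstructured residual is partly a matter of preference and has a small price. If variances and correlations are in fact equal, moving from (43 − 1)·2 = 84 to 42 degrees of freedom raises the critical t from 1.989 to 2.018, and 2.018/1.989 makes intervals about 1.5% wider. The parameter counts need no assumption; the sizes rest on assumed correlations and simulated data.
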